17.3 Serious Adverse Event (SAE) Reporting

An adverse event is considered serious if it results in ANY of the following outcomes:

- Death
- A life-threatening adverse event
- An adverse event that results in inpatient hospitalization or prolongation of existing hospitalization
- A persistent or significant incapacity or substantial disruption of the ability to conduct normal life functions
- A congenital anomaly/birth defect
- Important Medical Events (IME) that may not result in death, be life threatening, or require hospitalization may be considered serious when, based upon medical judgment, they may jeopardize the patient or participant and may require medical or surgical intervention to prevent one of the outcomes listed in this definition

Note: Hospital admission for a planned procedure/disease treatment is not considered an SAE.

SAE reporting is required as soon as the participant starts investigational treatment/intervention. SAE reporting is required for 30-days after the participant's last investigational treatment/intervention. Any event that occurs after the 30-day period that is unexpected and at least possibly related to protocol treatment must be reported. Please note: Any SAE that occurs prior to the start of investigational treatment/intervention and is related to a screening test or procedure (i.e., a screening biopsy) must be reported.

Please note: Any SAE that occurs prior to the start of investigational treatment/intervention and is related to a screening test or procedure (i.e., a screening biopsy) must be reported.

All SAEs must be submitted in PIMS. If an SAE requires submission to the HRPP office per IRB SOP RR-408 'Reporting of Serious Adverse Events', the SAE report must be submitted within 5 calendar days of the event. All other SAEs must be submitted within 30 calendar days of the event.

The report should contain the following information:

- The date the adverse event occurred
- The adverse event
- The grade of the event
- Relationship of the adverse event to the treatment(s)
- If the AE was expected
- Detailed text that includes the following
 - An explanation of how the AE was handled
 - A description of the participant's condition
 - Indication if the participant remains on the study

- If an amendment will need to be made to the protocol and/or consent form
- If the SAE is an Unanticipated Problem

17.2.1

Any additional SAE reporting information required by the sponsor or drug supplier should be included in this section.

17.2.2 Abnormal Laboratory Values

An abnormal laboratory value is considered to be an AE if the abnormality:

- Results in discontinuation from the study
- Requires treatment, modification/interruption of the chemotherapy dose or any other therapeutic intervention
- Or is judged to be of significant clinical importance. Clinically insignificant symptoms or findings will not be collected in the assessment note, or be graded or attributed on the toxicities forms.
- Considered Grade ≥2, per CTCAE version 4.0

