4.3 Intervention

4.3.1 Cisplatin Administration

Cisplatin treatment should be initiated following study registration. The starting dose of cisplatin is established as 25 mg/m² ivpb once a week (\pm 3 days) for 1-2 weeks prior to radiation. Dose modification following the first dose of cisplatin is subject to the discretion of the treating physician. Dosing calculation guidelines will follow MSKCC policies described on the website:

http://mskweb5.mskcc.org/intranet/shared/pharmacy/guidelines/Chemo_Guidelines/Manuals/Cisplatin.html

Cisplatin may be initiated immediately following simulation but prior to first radiation fraction. The rationale is so that the patient may initiate a form of treatment while waiting 1-2 weeks for radiation treatment planning to be completed.

Cisplatin may cause myelosuppression or other known non-hematologic toxicities. Following the completion of RT, pending no toxicities, but prior to the week 12 post RT evaluable timepoint, patients will continue to receive cisplatin based on MD discretion, or until POD.

The starting (first) dose of cisplatin will be 25 mg/m² ivpb once a week (\pm 3 days). Following the first dose of cisplatin, a CBC will be drawn once a week (\pm 3 days) prior to treatment to ensure treatment parameters are met. A comprehensive panel and Mg++ level will be obtained on D15 (\pm 3 days) of every cycle of cisplatin; these values will inform the dose for the following cycle of cisplatin. The length of one cycle of Cisplatin is 21 days. If cisplatin is withheld, the cycle count for treatment is also held. Based on the laboratory values drawn from the prior week's bloodwork, if the following parameters are met, cisplatin should be held as directed.

- If ANC is <1,000 mcL and/or platelets are <100,000 mcL, withhold cisplatin therapy for one week and repeat measurements. Physicians have the option of administering growth factor support during the time when ANC < 1,000 mcL or platelets are < 100,000 mcL. The treating MD may modify the subsequent cisplatin doses at their discretion. If there is a delay of 3 consecutive weeks of treatment due to toxicity, then the patient must discontinue protocol therapy and be removed from the study.
- If the ANC is still <1,000 mcL or platelets are 75,000-99,000 mcL, then hold weekly cisplatin again until the ANC is >1,000 mcL and platelets are >100,000 mcL. The treating MD may modify the subsequent cisplatin doses at their discretion.

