11.1 TOXICITIES/SIDE EFFECTS

A severe toxicity will be defined as any grade 3 toxicity, attributed to radiation or chemotherapy, which can be observed within 2 months of completion of protocol radiation. Toxicities will be assessed using the CTEP Version 4.0 of the NCI Common Terminology Criteria for Adverse Events (CTCAE version 4.0) at the website:

http://ctep.cancer.gov/protocolDevelopment/electronic_applications/ctc.htm. Patients will be assessed for toxicities until progression or death. Only adverse events that are possibly, probably or definitely related to protocol therapy will be documented on the CTCAE toxicities form and will be collected for data entry. Only hematologic toxicities that are considered Grade ≥ 2 , per CTCAE version 4.0 will be captured for this trial.

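### Section 17.2.2 makes a laboratory abnormality that interrupts or ends treatment an AE at any grade, but Section 11.1 captures hematologic toxicity only from grade 2, so lower-grade events that altered treatment can be missing from the toxicity endpoint

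*Combined protocol and SAP*

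**What the plan says.** Section 17.2.2 gives a list of criteria under which an abnormal laboratory value is an AE. Two depend on what happened to treatment: "Results in discontinuation from the study" and "Requires treatment, modification/interruption of the chemotherapy dose or any other therapeutic intervention". Neither mentions a grade. Grade is a separate item in the list: "Considered Grade ≥2, per CTCAE version 4.0".

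Section 11.1 sets the collection rule: "Only hematologic toxicities that are considered Grade ≥ 2 , per CTCAE version 4.0 will be captured for this trial". It makes no exception for events that delayed or stopped cisplatin. The same section limits the CTCAE form to events at least possibly related to protocol therapy.

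Section 4.3.1 states when counts interrupt treatment. The platelet instruction reads "platelets are <100,000 mcL, withhold cisplatin therapy for one week and repeat measurements". A further hold applies at 75,000-99,000 on repeat measurement. A "delay of 3 consecutive weeks of treatment due to toxicity" takes the patient off protocol therapy and off study. Section 13.0 also removes patients for a three-week chemotherapy delay for any reason, with a case-by-case allowance for holidays, vacation and unforeseen circumstances.

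Toxicity of concurrent cisplatin and radiation is a secondary objective in Section 2.0. Section 14.0 makes CTCAE v4.0 toxicities a secondary endpoint, to be compared by HRR status.

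**The concern.** The two sections do not agree on whether a hematologic abnormality below grade 2 belongs in the trial data when it interrupts cisplatin. Under 17.2.2 it is an AE because of its consequence. Under 11.1 it is left out because of its grade. No other section says which rule governs.

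The events at stake are those with a direct bearing on tolerability: a count low enough to hold a dose or, if it persists, to take the patient off study. If 11.1 is followed literally, a patient could be removed for toxicity while the toxicity data show no hematologic event. Section 14.0 has no early stopping rule, on the ground that tolerability can be extrapolated from head and neck and gynecologic cancers. The captured toxicity data are therefore a main means of checking that expectation in this population.

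**Working it through.** The plan gives no figure to reproduce. The check is a comparison of rules and thresholds.

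**1. The rules side by side, for a hematologic value below grade 2 that holds cisplatin**

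| Section | Test applied | Result |
|---|---|---|
| 17.2.2 | Did it interrupt chemotherapy or cause discontinuation? | AE |
| 11.1 | Is it grade 2 or higher? | Not captured |

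This mismatch does not depend on where CTCAE sets its cut-offs. It does depend on reading the 17.2.2 items as alternatives, which is the natural reading because grade stands as its own item. If grade 2 were instead a joint condition on all items, the two sections would agree, but a lower-grade event that held treatment would still go uncaptured under 11.1.

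**2. Whether the protocol's own thresholds can produce such an event**

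Let *c* be the platelet count below which CTCAE v4.0 assigns grade 2. The documents adopt CTCAE v4.0 but do not print *c*, so it is an assumption.

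- Cisplatin is held when platelets < 100,000 (Section 4.3.1).
- Thrombocytopenia is captured when platelets < *c* (Section 11.1).
- Held but not captured: *c* ≤ platelets < 100,000.

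| Assumed *c* | Platelet range held but not captured |
|---|---|
| 50,000 | 50,000 to just under 100,000 |
| 75,000 (lower edge of the protocol's repeat-hold band) | 75,000 to just under 100,000 |
| 90,000 | 90,000 to just under 100,000 |
| 100,000 or higher | none |

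The gap closes only if grade 2 begins at 100,000 or higher. Section 6.2 requires platelets above 100,000 at entry, so a fall into the gap would happen after that screening count.

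**3. From a hold to removal**

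With *c* = 75,000, a patient whose platelets stay at 75,000-99,000 is held, held again on repeat testing, and removed once the delay reaches three consecutive weeks. If no other hematologic toxicity reached grade 2, that patient contributes nothing to the captured hematologic toxicity data.

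**4. What the capture rule does not touch**

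- Severe toxicity in Section 11.1 is defined at grade 3, above the floor.
- SAE reporting in Section 17.3 depends on seriousness, not on this floor.
- The primary endpoint is radiographic CR.
- Sample size, power and type I error do not enter.

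**The case against.** The strongest reply is that 17.2.2 defines an AE while 11.1 decides which toxicities to collect. Section 11.1 is openly selective, since it also drops unrelated events, and collecting a subset is a legitimate design choice. In addition, the Section 10.0 footnotes require toxicities to be recorded with grade, attribution and dates, weekly during RT and on day 1 of cycles, with no grade floor, and CBCs are weekly during cisplatin. So the information should exist at source.

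Part of this stands. The counts are probably recoverable, and holds and removals may appear in dosing or off-study records. But the footnotes do not override the word 'only' in 11.1, and nothing says that dosing or off-study records feed the toxicity endpoint.

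Four stronger readings are tempting, and the documents do not support them.

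- **A numerical loss.** Section 11.2 puts myelosuppression at 25-30% of cisplatin patients, which for 54 patients would be 54 × 0.25 = 13.5 to 54 × 0.30 = 16.2. That cannot be turned into a count of lost events. The text gives no grade distribution and no share confined to the platelet band. It says cytopenias are more pronounced at doses above those used here. A patient with another hematologic event of grade 2 or higher would still be counted.
- **No other measure of tolerability.** Severe toxicity, SAE reporting and the removal criteria all bear on it.
- **A contradiction inside 17.2.2.** The sentence "Clinically insignificant symptoms or findings will not be collected in the assessment note, or be graded or attributed on the toxicities forms" sits within the clinical-importance item and is most naturally read as qualifying that item. Grade 2 or higher is a separate item, so such a value is an AE on its own.
- **A biased comparison by HRR status.** The floor applies equally to both groups, and nothing in the text points to a differential effect.

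**Conclusion.** The mismatch between 17.2.2 and 11.1 is real and unreconciled. Followed as written, 11.1 can leave a hematologic event that held cisplatin or ended participation out of the secondary CTCAE toxicity endpoint. For platelets of 75,000-99,000 this requires that the band lie below CTCAE v4.0 grade 2, which the documents do not state. If the band is grade 2, nothing in it is lost.

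The size of the loss cannot be estimated from the documents and may be zero. The removal scenario is narrow: it needs a sustained low count and no other captured hematologic toxicity. The effect is confined to toxicity reporting below grade 2. This is a data-capture inconsistency worth correcting, not a threat to the primary analysis.

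**What to change.** Reconcile the two sections through the capture rule.

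- **Section 11.1:** capture hematologic toxicities that are grade 2 or higher, or of any grade if they led to a cisplatin hold, dose modification, treatment or removal from study. These are the action-based criteria already in 17.2.2. The existing limit to treatment-related events can stay.
- **Section 14.0:** report the number of patients with at least one such treatment-altering hematologic event alongside the grade 2 or higher rates, so that the two measures remain separate.

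The change concerns recording and reporting only. The hold and removal rules in Sections 4.3.1 and 13.0 are untouched.

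The cost is a wording amendment and a few more form entries, drawing on CBCs that are already required weekly. The reported hematologic toxicity rate may come out slightly higher; showing the two measures separately makes the reason visible.

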18.0 INFORMED CONSENT PROCEDURES

Before protocol-specified procedures are carried out, consenting professionals will explain full details of the protocol and study procedures as well as the risks involved to participants prior to their inclusion in the study. Participants will also be informed that they are free to withdraw from the study at any time. All participants must sign an IRB/PB-approved consent form indicating their consent to participate. This consent form meets the requirements of the Code of Federal Regulations and the Institutional Review Board/Privacy Board of this Center. The consent form will include the following:

1. The nature and objectives, potential risks and benefits of the intended study.
2. The length of study and the likely follow-up required.
3. Alternatives to the proposed study. (This will include available standard and investigational therapies. In addition, patients will be offered an option of supportive care for therapeutic studies.)
4. The name of the investigator(s) responsible for the protocol.
5. The right of the participant to accept or refuse study interventions/interactions and to withdraw from participation at any time.

Before any protocol-specific procedures can be carried out, the consenting professional will fully explain the aspects of patient privacy concerning research specific information. In addition to signing the IRB Informed Consent, all patients must agree to the Research Authorization component of the informed consent form.

Each participant and consenting professional will sign the consent form. The participant must receive a copy of the signed informed consent form.

